**4.4b. Randomization:** Individuals who have SDB based on the diagnostic PSG will be randomly assigned to receive the BEST program or the control condition (See below) using a randomized block design based on level of injury (cervical or thoracic). Participants and research staff (except intervention staff) will be blinded to group assignment. It may be difficult to keep assessment research staff blinded to group assignment if participants inadvertently describe the intervention. Furthermore, assessment staff will be blinded to study research questions, and study documents (e.g., consent forms) will indicate we are comparing "two programs to help patients with SDB" and participants will be blinded to the content of the intervention program they do not receive. We have successfully achieved blinding of assessment staff in prior research by controlling for "observable" aspects of the intervention program (e.g. frequency of contacts). In this way, "double blinding" can be achieved in behavioral treatment trails. Randomization procedures will follow the CONSORT criteria for randomized trials. [name] (statistician) will generate the randomization sequence for each block, and two sets of envelopes containing group assignment will be generated. The envelopes will be sealed and stored in the office of the study's statistical clerk where the intervention and assessment staff will not have direct access. Only Drs.

[name] and [name] and intervention staff will have access to the randomization envelopes. Once final eligibility is determined, the next envelope in the sequence for the appropriate block will be opened and that will determine the intervention group to which the participant is assigned. This will be communicated to the appropriate Research Staff.

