Mixed-effects models will be used to compare monthly PAP adherence rates for the BEST program versus control program. When applied to longitudinal designs, mixed-effects models accommodate incomplete data across time points (such as arises in this study where only some participants will have data beyond six months) and can permit specification of a wide variety of residual covariance structures. PAP adherence will be analyzed using a 2 by 12 factorial mixed-effects model with a fixed intercept, where treatment group is a two-level between subjects factor (i.e., BEST versus control) and time is a 12 level categorical repeated measures factor (i.e., month 1, month 2, ... month 12). This approach will allow us to examine potential non-linear trends in the data which would not be readily apparent if time were treated as a continuous variable. The Bayesian Information Criteria (BIC) will be used to identify and select the best fitting residual covariance structure. Using the mixed-effects model, the difference in adherence rates between the BEST program and control group will be assessed and tested at each month.

Hypothesis 1a will be assessed evaluating the significance of the difference in adherence rates between the BEST program and control groups in months 1-3 (during the BEST program intervention).

Hypothesis 1b will be assessed by testing the significance of the difference in adherence rates between the BEST program and control groups in months 4-6 (after the BEST program has ended).

**Figure 6** illustrates four possible patterns of results Pattern 1 suggests the BÉST program immediately improved PAP adherence and effects were sustained over time. Pattern 2 shows that the BEST program improved PAP adherence during the treatment period; however, effects later diminish. Pattern 3 shows that the

BEST program improved PAP adherence gradually during the "treatment" period and effects were sustained over time. Pattern 4 also shows that the BEST program improved PAP adherence gradually; however, effects later diminished, These patterns will be statistically dissected to distinguish between immediate vs. gradual gains in pap adherence during the "treatment" phase, and between "sustained" and "diminishing" effects during the posttreatment phase (refer to [name] 2012).

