**Data Analysis for Hypotheses 2a-d.** These hypotheses will be tested using ANCOVA models to compare groups (BEST vs. control) for each of main outcome measured at post-treatment, after adjusting for baseline measurement of the outcome as a covariate. Compared to a "split-plot ANOVA" or an analysis of change scores, this strategy offers greater statistical power and better controls for possible baseline differences.

**Power Analysis for Hypotheses 2a-d. Table 7** shows the required sample size as a function of the standardized effect size and the correlation between posttest and baseline scores to achieve 80% power using a two-tailed alpha of 0.05. Cohen describes an effect size of d=0.8 as large, d=0.5 as medium, and d=0.2 as small. **Table 7** focuses on the combination of effect sizes and pretest-posttest correlations that would achieve power of .80. To evaluate plausible pretest-posttest correlations for the measures associated with hypotheses 2a-c, we assessed baseline to 4-month follow-up measures in a RCT of a sleep intervention for Veterans with disabilities. These are presented in detail below for each of the three hypotheses. **Table 7** shows that under the most pessimistic scenario (assuming no correlation between pre-test and post-test measures), this study has sufficient power to detect a large effect (*d*=0.75). As the purpose of this study is to find clinically meaningful effects (i.e., effects that tend to be large), this power analysis suggests sufficient power to detect such effects for all outcome measures. However, our prior research found very substantial pretest/posttest correlations (e.g., r=.75) which would permit detection of smaller effects (i.e., medium effects of d=0.50). Using the lower confidence limits still found substantial correlations (e.g., r=0.56) suggesting that this study will have the ability to detect all effects of d=0.63 or larger with a sample size of n=56 with complete 3-month follow-up data. To achieve this, we will randomize 62 subjects into intervention vs. control.

**Table 7**. Required total sample size as afunction of effect size and pre-test/post-testcorrelation for 80% power, alpha=.05.

Sample	Effect Size	Pretest/Posttest
Size	(Cohen's d)	Correlation
	d=0.50 (medium)	r=0.75
N=56	d=0.55	r=0.68
N-50	d=0.60	r=0.60
	d=0.63	r=0.56

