Hypothesis 2a: To estimate the pretest-posttest correlation, we used our prior research showing a baseline-4-month correlation for PSQI of r=0.74 (95% CI=[.56,.86], N=40). Choosing

d=0.65	r=0.50
d=0.70	r=0.36
d=0.75	r=0.00

the lower confidence limit (r=.56) implies sufficient power to detect an effect size of Cohen's d=.63 (an effect somewhat larger than a medium effect) with N=56 (**Table 7**). Choosing the observed correlation (r=.74) implies sufficient power to detect an effect size of Cohen's d=.50 (a medium effect). Assuming no correlation (r=0.00), the study could still detect an effect size of Cohen's d=.75 (a large effect).

Hypothesis 2b: In the same preliminary data we found the baseline-4-month correlation of instrumental measures of daily living (IADLs) was r=.81 (95% CI=[.67, .89[). Using the lower confidence limit suggests the ability to detect an effect of d=.55 (slightly larger than medium effect).

Hypothesis 2c: To inform the power for this hypothesis, we examined baseline-4-month correlations for PHQ9 and FSS in our prior work. The correlation for PHQ9 was r=.79 (95% CI=[.64,.89], N=40), and for FSS, r=.76 (95% CI=[.57,.87], N=36). Using a conservative approach (lowest lower confidence interval = 0.57), an effect size of 0.63 could be detected with a sample size of 56 (See **Table 7**). Assuming the lowest observed correlation (r=0.76), the study would have sufficient power to detect an effect of d=0.50 (a medium effect). Our **Preliminary Data** shown in section 3.6 indicate large treatment effects comparing a behavioral sleep program vs. attention-control in terms of FSS ( $\omega^2$ =64%) and PHQ9 ( $\omega^2$ =35%). We believe similarly "large" effects for these outcomes are likely in the proposed study.

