Does Treatment Of Sleep-Disordered Breathing Improve Functional Outcomes In SCI?

Data Analysis Plan

NCT02830074

Approved Date April 2, 2020

DATA ANALYSIS PLAN

Data analysis plan for primary outcomes:

Data Analysis for Aim 1: This aim examines the effects of the BEST program on PAP adherence. The main outcome will be the number of nights (out of 90 nights) with >4 hours of PAP use (measured by the PAP machine itself). Hypothesis 1 will be assessed using a two-sample t-test to compare PAP use for the BEST program vs. control program. Because adherence data will be gathered remotely using telemonitoring technologies in which PAP machines transmit use data to a cloud-based server, complete data is expected for each person.

Data analysis for Aim 2: This aim compares outcome measures assessed at 3-months that are expected to improve as a result of the BEST program. These outcomes will be -- 1) Subjective Sleep Quality Measured by The Pittsburgh Sleep Quality Index (PSQI); 2) Quality of Life as Measured by WHO-QOL BREF Questionnaire, 3) Respiratory Function: Spirometry and Respiratory Muscle Force, 4) Functional Status as Measured by CHART Questionnaire, 5) Depressive Symptom Severity as measured by the Patient Health Questionnaire-9 (PHQ-9); 6) Fatigue Symptoms as measured by Flinders Fatigue Scale; 7) Sleepiness as measured by the Epworth Sleepiness Scale. For each outcome measure, a two-sample t-test will be used to compare PAP use for the BEST program vs. control program.

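### Injury level stratifies the randomisation but appears in no planned analysis; adding it as a covariate is a nearly free precision gain if it is prognostic

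*Protocol*

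**What the plan says.** **Allocation (Protocol 4.4b).** Participants with SDB are randomised "using a randomized block design based on level of injury (cervical or thoracic". The word block here means the injury-level stratum: the statistician "will generate the randomization sequence for each block, and two sets of envelopes containing group assignment will be generated", and at allocation "the next envelope in the sequence for the appropriate block will be opened". No permuted-block size is given within strata.

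**Analysis.**
- Protocol 4.6b, Aim 1: a mixed-effects model "where treatment group is a two-level between subjects factor" and month is the repeated factor. It has no injury-level term.
- Protocol 4.6c, Aim 2: ANCOVA comparing the arms "after adjusting for baseline measurement of the outcome as a covariate". It has no injury-level term.
- SAP, Aim 1: "Hypothesis 1 will be assessed using a two-sample t-test to compare PAP use for the BEST program vs. control program".
- SAP, Aim 2: "For each outcome measure, a two-sample t-test will be used".
- Protocol 4.6d, exploratory Aim 3: depression, insomnia and bladder dysfunction are given as example subgroups. The list is open, but injury level is not on it, and subgroup interaction tests would not make it a covariate in the main analyses.

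The one stated reason to think injury level matters is in Protocol 4.3, which says that SDB is more common with cervical injury.

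**The concern.** A factor is normally stratified on because it is expected to be prognostic. If injury level does predict adherence or a 3-month outcome, a model that omits it leaves the between-stratum variance in the error term. Power is then lower than the same data could give. If the arms are balanced within strata, the reported standard error is also too large for the design: the t-test rejects too rarely under the null and its confidence intervals are too wide. At stake is some precision in a small trial (62 randomised, 56 expected to complete). A lesser point is that Protocol 4.4d collects demographic data partly as candidate covariates without naming any for the models, so prespecifying the stratum would also settle in advance whether to adjust for it.

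**Working it through.** **Inputs from the documents.** Two-sided alpha 0.05 and 80% power; 62 randomised (31 per arm), 56 with complete data (28 per arm); d=0.75 paired with zero baseline correlation (Protocol 4.6c: "Assuming no correlation (r=0.00), the study could still detect an effect size of" 0.75); d=0.63 at r=0.56 and d=0.50 at r=0.74; Aim 1 SD 0.0913 and a 10% difference.

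**Assumed input.** R², the share of outcome variance explained by injury level, is not in the documents. The values 0, 0.05, 0.10 and 0.20 are used.

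**Step 1: the plan's own figures.** Per-arm n = 2(1.960+0.842)²(1−r²)/d². At d=0.75, r=0 this is 2×7.85/0.5625 = 27.9, so 28 per arm and N=56, as stated; the other pairs in Table 7 also give 56. Power is 80.1% by the normal approximation and 78.7% by noncentral t on 54 df. For Aim 1, d = 0.10/0.0913 = 1.095 with 28 per arm gives 98.1% by noncentral t, against the stated 98%.

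**Step 2: power with the stratum added.** With arms balanced within strata, residual variance falls from 1 to 1−R² and one df is lost (54 to 53). The noncentrality is d√(n/2)/√(1−R²), where d√(n/2) = 0.75×√14 = 2.806.

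| R² | Noncentrality | Adjusted power |
|---|---|---|
| 0 | 2.806 | 78.7% |
| 0.05 | 2.879 | 80.7% |
| 0.10 | 2.958 | 82.7% |
| 0.20 | 3.137 | 86.9% |

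**Step 3: the unadjusted t-test under balance.** The difference in means has variance (1−R²)(2/n), but the t-test estimates about 2/n. Its actual size is therefore roughly P(|Z| > 1.96/√(1−R²)):
- R²=0.05: cut-off 2.011, size 4.4%
- R²=0.10: cut-off 2.066, size 3.9%
- R²=0.20: cut-off 2.191, size 2.8%

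**Step 4: simulation of both tests.** 40,000 trials per cell, total variance 1, equal strata, 56 completers, d=0.75. The blocked and simple rows randomise 62 and keep 56 at random. Each list runs over R² = 0/0.05/0.10/0.20.

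| Allocation within strata | t-test power % | With stratum % | Gain (points) | t-test type I % |
|---|---|---|---|---|
| Exact balance | 78.3/79.3/80.0/81.2 | 78.3/80.8/82.8/87.0 | 0/1.5/2.8/5.8 | 5.1/4.5/3.8/2.8 |
| Permuted blocks of 4 | 78.9/79.3/79.5/80.4 | 78.8/80.6/82.6/86.7 | −0.1/1.3/3.1/6.3 | 5.1/4.6/4.1/3.1 |
| Simple | 78.1/77.9/77.8/77.9 | 77.3/79.3/81.4/85.6 | −0.8/1.4/3.6/7.7 | 5.0/5.3/5.2/5.0 |

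The adjusted model's type I error stays between 4.9% and 5.2%. Monte Carlo error is at most 0.25 point for power and 0.11 for type I error. Strata split 75:25 give the same picture. At d=0.63 the gains are about 2, 4 and 8 to 9 points for R² = 0.05, 0.10 and 0.20.

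**Step 5: Aim 1, 62 participants with complete data.** At the protocol's own effect (d=1.095) power is already about 99%, and the gain is at most 1.0 point. If the true standardised effect were 0.75, the gain would be −0.1/1.4/2.7/5.0 points (blocks of 4) or −0.7/1.3/3.5/6.8 (simple). Treating the outcome as a bounded count of nights out of 90, with an assumed between-person SD of 0.33, gives nearly the same. For the mixed model with complete data for months 1–3 and a random intercept, the group contrast averaged over months equals a linear model on person means, so these figures carry over to that case only.

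**Step 6: Aim 2 with the baseline outcome in the model.** The stratum effect is taken to be the same at baseline and follow-up. At r=0.56, d=0.63 the gain from adding the stratum is −0.1/0.3/0.8/2.3 points (balanced) or −0.8/−0.2/0.5/2.1 (simple). At r=0.74, d=0.50 (balanced) it is under 1 point.

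**The case against.** The strongest reply is that nothing here is an error. The treatment estimate is unbiased, false positives are not inflated, and the t-test stays within about 2 points of its planned 80% in every case at d=0.75. All of that stands.

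The benefit also rests on an undocumented R². The only stated link is with SDB prevalence, and everyone randomised already has SDB. This stands too, so the R²=0.20 figures mark the top of an assumed range and are not an expectation.

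For Aim 2, the larger loss comes from the SAP dropping the protocol's baseline adjustment. By noncentral t at 28 per arm, restoring it lifts power from 64% to 80% (d=0.63, r=0.56) and from 45% to 78% (d=0.50, r=0.74). The stratum adds little after that. This is right, and it makes the stratum secondary for Aim 2.

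For Aim 1, the gain is negligible at the protocol's stated SD. With the assumed SD of 0.33, the protocol's 10% threshold for clinical relevance is d of about 0.30; at N=62 power is then about 22% unadjusted and 22–26% adjusted, so the stratum does not rescue that comparison.

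Finally, the conservatism of the t-test requires balance within strata, which section 4.4b suggests but does not fix.

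These arguments limit the weight of the point. They do not remove it: the factor is absent from every specified model, and including it costs almost nothing.

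**Conclusion.** The point holds as a minor matter of efficiency. In the SAP's Aim 2 t-tests at d=0.75, omitting the stratum gives up roughly 1.5 points of power if injury level explains 5% of outcome variance, about 3 to 4 if it explains 10%, and about 6 to 8 if it explains 20%. With baseline-adjusted ANCOVA the loss is about 2 points at most, assuming the stratum effect is stable over time; it would be larger if injury level explained variance beyond the baseline score. At the protocol's own Aim 1 effect it is at most 1 point. If R² is zero there is no loss. The t-test is conservative only if allocation is balanced within strata. The mixed-model equivalence was checked for complete months 1–3, not for the incomplete later months or a covariance structure chosen by BIC.

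**What to change.** Prespecify the randomisation stratum, as used to draw the envelope, as a fixed covariate in every between-group analysis:
- **Aim 1:** a linear model with group and stratum in place of the t-test, or group by month plus stratum if the mixed model is used.
- **Aim 2:** group, baseline value of the outcome, and stratum.

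The cost is one line in the SAP and one degree of freedom. No new data are needed, because the stratum is known for everyone randomised. If injury level turns out not to be prognostic, the simulated power loss is about 0.1 to 0.2 point with balanced or blocked allocation and up to about 0.9 point with simple randomisation within strata.

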#### Sleep Measures:

Laboratory Polysomnography (PSG): Participants will be studied in our specially-equipped sleep laboratory at the JDDVAMC using a wireless PSG system (**Figure 1**, above). The recording will include a standard clinical PSG montage, including EEG, EOG and EMG for sleep staging, and respiratory effort and airflow for evaluation of sleep disordered breathing. In addition, end tidal PCO2 (PETCO2) will be measured to identify hypoventilation during sleep. Sleep parameters will be recorded continuously from bedtime to rise time on the night of PSG. Sleep and respiration will be scored using standard AASM criteria. The Apnea Hypopnea Index (AHI) will be computed as the number of apneas + hypopneas per hour of sleep. Sleep disordered breathing will be defined by an AHI≥5 events per hour of recorded sleep, using the AASM's standard scoring criteria.

Sleep Questionnaires: We will use the Insomnia Severity Index (ISI) to assess insomnia symptoms. The ISI is a 7-item instrument using Likert-type scales that measure perceived severity of insomnia symptoms from 0 (not at all) to 4 (very much). The ISI correlates well with the PSQI (r=.67), and sleep diary measures (r's=.32-.91). The Usability of Sleep Apnea Equipment-P (USE-SA(P) version 3.0) will be used to assess PAP usability at the 3-month follow-up. The self-administered questionnaire contains 18 items that measure 5 aspects of PAP equipment usability, including learnability, memorability, efficiency, device feedback, and satisfaction. An additional 7 items assess the frequency of usability issues, and 3 items ask about equipment features.

#### Main Outcome Measures:

The Pittsburgh Sleep Quality Index (PSQI) is an 18-item questionnaire that assesses sleep quality and disturbances over the past month. The PSQI is sensitive for distinguishing normal and abnormal sleepers and has good test-retest reliability. We will use the 3-factor scoring, which has been shown to have superior psychometric properties compared to the original 7-factor scoring system. This will be used as the main independent measure of sleep quality.

Sleep diaries will be completed for 1 week before the laboratory PSG, and again at the 3-month follow-up assessments. We will use a diary based on the AASM Consensus Sleep Diary, with items added to track sleep medication use and sleepiness and fatigue ratings (0-10 point visual analog scales), and self-reported PAP use. The diary will be used to compute self-reported sleep efficiency (time asleep out of total time in bed), hours of sleep, time to fall asleep, time awake at night, and number of awakenings. This will be used as an independent measure of sleep quality. Participants who cannot complete the paper/pencil diary will be provided with a telephone number they can call to report diary information each morning.

PAP adherence will be monitored remotely using existing data gathering systems. This will be summarized into the proportion of nights (out of 90 nights) with use  $\geq$ 4 hours. We will also examine mean hours of nightly use for each participant over the 90-day intervention period. We have experience using these procedures in other studies and this process has resulted in data loss rates <10% for PAP use. the proportion of nights (out of 90 nights) with use  $\geq$ 4 hours will be used as the main independent measure of PAP use.

The Spinal Cord Independence Measure-Self Report (SCIM-SR) will be used to evaluate performance of activities of daily living. The SCIM-SR is a self-report version of the SCIM III, a reliable and valid measure of global disability for patients with SCI/D. The SCIM–SR has 3 subscales: self-care, respiration and sphincter management, and mobility. Scores range from 0-100 and higher scores reflect greater independence. Comparison of the SCIM-SR to the SCIM III showed high correlations between the scales (Pearson's r for the total score=.87; subscales=.81-.87). Since some individuals' in the study will require the assistance of family members or caregivers, for descriptive purposes we will also ask an individual familiar with the patient's level of functioning to complete the SCIM if the patient gives permission for us to do so. The SCIM-SR total and subscales scores (as completed by the patient) will be used as the functional status outcome measure.

The WHOQOL-BREF is a 26-item version of the WHOQOL-100, and is frequently used as an outcome measure in clinical trials. The questionnaire is composed of four domains: physical health, psychological health, social relationships and environment. It also includes one question on overall quality of life and one on general health. Importantly, items on this scale are not dependent on mobility, which is unlikely to change in patients with

SCI/D as a result of improved sleep. The WHOQOL-BREF scores correlate highly (.89 or above) with WHOQOL-100 scores, and demonstrate good discriminant validity, content validity, internal consistency and test-retest reliability. The four WHOQOL-BREF domain scores will be used as main outcome measure.

The Patient Health Questionnaire-9 (PHQ-9) is a 9-item depression module in the PHQ (a self-administered diagnostic instrument for common mental disorders) which is part of the Primary Care Evaluation of Mental Disorders (PRIME-MD) suite of evaluation tools. The PHQ-9 aligns to the DSM-IV diagnostic criteria for depression and is widely used to screen for depression across VA. The PHQ-9 total score will be used to measure depressive symptom severity as an outcome.

The Flinders Fatigue Scale (FFS) is a 7-item fatigue rating scale used to measure general symptoms of fatigue. The FFS has high internal consistency (.91), can discriminate good versus poor sleepers (p<.0001) and is sensitive to change over time. The FSS is sensitive to change after sleep-related interventions as well. The FSS total score will be used as an outcome measure.

Spirometry is a simple bedside test used to evaluate lung function. Key spirometry values include forced vital capacity (FVC) and forced expiratory volume over 1 second (FEV1) and the absolute FEV1/FVC ratio. If the FVC and FEV1 are decreased, the absolute FEV1/FVC ratio distinguishes between obstructive and restrictive impairments. A normal absolute FEV1/FVC ratio suggest that restrictive ventilatory impairment may be present, and a reduced FEV1 and absolute FEV1/FVC ratio indicates an obstructive ventilatory pattern. We will use supine FVC and MIP as the key outcome measures for respiratory function for this study, as these are the most representative of respiratory functioning during sleep.

